# A

industries that market agents for treating insomnia.

## Power Considerations:

We conducted power calculations for the study proposed using data from our previous two studies that compared reaction time performances of PI and NS participants. From the archival data sets used for these studies we obtained estimates of mean response latencies (reaction times) correct response rates and error rates for PI and NS groups to estimate the sample size needed to test the 2 study hypotheses. All power calculations were conducted using the proc power procedures available in SAS, version 9.2.

Hypothesis 1 entails testing the simple main effect of group membership (PI vs. NS) on neuro-cognitive performance. As a proxy for global performances we used response latency, correct response rate and error rate data derived from our 2008 study and our above referenced pilot study. Those studies showed the following information in comparisons of our hyperaroused PI group and normally alert NS group.

Measure	PI group	NS group	Sample standard deviation
Mean response latency - msec	470.6	420.8	112.1
Mean # correct responses	75.7	77.5	3.74
Means # errors	4.46	2.60	3.45

Given these data and assuming  $\alpha = .05$ , and 82 subjects in each of these two groups we would have a .93 power to detect the predicted group differences in their mean error rates across trials, .87 power to detect the predicted differences in mean correct response rates, and .81 power to detect the predicted differences in mean reaction time latencies.

Hypothesis 2 entails testing the interaction term showing that difficult reaction time tasks will show significant differences between PI and NS whereas simple tests will not. Basically this analysis ultimately will entail a posteriori contrasts that show PI vs. NS group differences on complex tasks but not simple tasks. Again we used response latency data obtained from our 2008 study for conducting power analyses for this hypothesis. Those data showed the following mean group differences and group standard deviations for complex and simple tasks.

Measure	PI group	NS group	Sample standard deviation
Complex test response latency - msec	496.65	438.14	133.4
Simple test response latency - msec	247.9	226.4	66.8

Given these data and assuming  $\alpha = .05$ , and 82 subjects in each of these two groups we would have a .80 power to detect the predicted group differences on complex tasks but only .54 power to detect group differences on the simple tasks.

On the basis of these calculations we will plan to enroll 82 hyperaroused PI sufferers and 82 NS in this study.

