# A

factorial analysis. Although our statistical model could also include "trials" as a factor, we have chosen to limit the complexity of our analyses by excluding this factor and using mean values of each of our performance measures across trials for each participant in our analyses. To further simplify our analyses we will compute mean values of our 5 dependent measures for the three simple tests and another set of mean values of these dependent measures for our three complex tests and use those composite means in all planned analyses.

Before conducting tests of the study hypotheses, we will conduct a number of preliminary 2 (PI vs. NS) x 2 (alert vs. sleepy) x 2 (simple vs. complex test) ANOVAs and cross tabs analyses to determine if the various "cells" of our study include participants who do not differ significantly in terms of their mean ages, years of education, gender compositions and racial/ethnic compositions. If study "cells" are found to differ significantly on any of these variables, those variables will be used as covariates in statistical models designed to test study hypotheses. If study cells do not differ in regard to these variables we will use unadjusted statistical models to test study hypotheses.

For study hypotheses 1 & 2, we will conduct 2 (PI vs. NS) x 2 (simple vs. complex test) MANOVAs/MANCOVAs analyses to test for statistical significance across the multiple performance measures derived from the neuro-cognitive test battery. If the MANCOVA/MANOVA shows significant results, univariate ANCOVAs/ANOVAs will be conducted to tests for similar significant effects for each individual performance measure (i.e., mean reaction time; within subject standard deviations for reaction time; error responses).

Hypothesis 1 will be tested via examination of the main effect of the *group factor* (PI vs. NS) in these analyses. Findings showing significantly slower and more variable reaction times, fewer correct responses and higher error rates in the hyperaroused PI group will support this hypothesis. Elimination of these statistical differences in repeat analyses that use hyperarousal scale scores as a covariate will confirm the role of hyperarousal in explaining the observed group differences.

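### The Hypothesis 1 powers (.93, .87, .81) are upper bounds: they are stand-alone t-test powers, while the plan tests each measure only after a significant MANOVA, whose power was not calculated

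*Combined protocol and SAP*

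**What the plan says.** The Power Considerations section gives a mean for each group and one standard deviation for response latency, correct responses and errors. At alpha .05 with 82 per group it then says "we would have a .93 power to detect the predicted group differences in their mean error rates across trials", followed by .87 for correct responses and .81 for latency. On method it says only that "All power calculations were conducted using the proc power procedures available in SAS, version 9.2". It describes the three measures as a proxy for global performance. It mentions neither a MANOVA nor any correlation between measures. From these calculations it concludes that "we will plan to enroll 82 hyperaroused PI sufferers and 82 NS in this study".

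The Statistical Plans section sets out a different route to a result. Hypotheses 1 and 2 are tested by 2 x 2 MANOVAs/MANCOVAs (group by test difficulty) across the performance measures, and then: "If the MANCOVA/MANOVA shows significant results, univariate ANCOVAs/ANOVAs will be conducted to tests for similar significant effects for each individual performance measure". Hypothesis 1 is read from the group main effect in those analyses.

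**The concern.** The power calculation and the analysis describe different procedures. The calculation treats each measure as if it had its own free-standing test. The analysis puts a multivariate test in front. If that test fails, no univariate test is run, even where the measure's own difference would have been significant.

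The chance of a positive finding on any one measure is therefore the chance that two tests both succeed, and it cannot exceed the printed figure. This holds for each measure separately, so it does not depend on whether Hypothesis 1 requires all the listed differences or only some of them.

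The stake is the sample-size justification, which rests on these figures. Latency is the measure with least room: its printed power is .81.

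**Working it through.** **Inputs from Power Considerations** (PI mean, NS mean, SD; 82 per group; alpha .05):
- latency: "470.6 420.8 112.1"
- correct responses: "75.7 77.5 3.74"
- errors: "4.46 2.60 3.45"

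Sidedness is not stated. Two-sided is assumed because it reproduces the printed figures; one-sided gives .96/.92/.88 for errors/correct/latency and does not.

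**Step 1: reproduce the printed powers.** d = |difference|/SD; noncentrality = d × √(82/2); 162 degrees of freedom; critical t = 1.975.

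| Measure | d | Noncentrality | Power | Printed |
|---|---|---|---|---|
| Errors | 1.86/3.45 = .539 | 3.45 | .929 | .93 |
| Correct | 1.8/3.74 = .481 | 3.08 | .865 | .87 |
| Latency | 49.8/112.1 = .444 | 2.84 | .807 | .81 |

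The figures reproduce and are single-outcome powers.

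**Step 2: add the gate.** For each measure, P(MANOVA significant and t-test significant) ≤ P(t-test significant). The values in Step 1 are therefore ceilings.

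**Step 3: size the loss.** The gate is modelled as the two-group Hotelling T² at .05. With p = 3 outcomes and N = 164, F = T² × 160/(162 × 3), compared with F(3,160) = 2.66. Its noncentrality is 41 × δ′R⁻¹δ, where δ holds the three d values (all signed so that worse is positive) and R is the correlation matrix. R is not in the documents and has to be assumed.

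One part of R has an indirect clue. Mean correct plus mean errors is 75.7 + 4.46 = 80.16 in PI and 77.5 + 2.60 = 80.10 in NS, so the two counts look near-complementary. I take their correlation as .95 after reversing the sign of correct, and vary the correlation r of latency with both.

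Joint power comes from simulation (200,000 runs per row):

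| r | Gate noncentrality | Gate power | Errors | Correct | Latency |
|---|---|---|---|---|---|
| -.3 | 28.7 | .997 | .93 | .86 | .81 |
| 0 | 20.4 | .975 | .92 | .86 | .80 |
| .2 | 17.3 | .946 | .91 | .85 | .79 |
| .3 | 16.1 | .929 | .89 | .84 | .79 |
| .5 | 14.2 | .892 | .87 | .82 | .77 |
| .7 | 12.8 | .856 | .85 | .80 | .76 |

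If the correct-error correlation is .9 instead, the r = .7 row becomes .83/.79/.75.

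The noncentrality shows the mechanism. Correct and errors together contribute .300 to δ′R⁻¹δ at every r. At r = 0 latency adds .197 (.300 + .197 = .498 before rounding; × 41 = 20.4). At r = .7 it adds only .012 (.313 × 41 = 12.8), because most of its difference is already predicted by the accuracy measures.

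**Step 4: more outcomes in the gate.** The plan lists five dependent measures, and its univariate step also names within-subject reaction-time variability. Take four outcomes (latency, correct, commission, omission), with the error effect split equally, commission and omission correlated .3, and correct-error .95. At r = 0/.3/.5/.7 gate power is then .96/.90/.86/.82, errors .92/.87/.84/.81 and latency .80/.77/.76/.73. Adding a variability measure with no unique information, correlated .6 with latency, gives latency .79/.76/.73/.70. Extra outcomes do not always lower gate power: the loss grows when they bring little information of their own.

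**The case against.** The printed powers contain no arithmetic error. They are right for the tests they describe, and the plan openly calls its three measures a proxy. That stands, and the point is about what the figures describe.

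A reader might infer that the planned procedure definitely lacks the stated power, that latency is definitely below .80, or that 82 per group is too few. The documents support none of these. They give no correlations and no commission/omission split, so the loss cannot be fixed. A speed-accuracy trade-off would make the latency-error correlation negative, and nothing in the documents rules that out. At -.3 there is practically no loss with three outcomes, and in the four-outcome model gate power is .995 with latency still at .81. Nor does the plan state an .80 target; that threshold is only a customary yardstick.

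Two further objections stand as limits. The plan does not say which outcomes enter the MANOVA. It also does not say which effect in the 2 x 2 model opens the gate. Reading it effect by effect, with the group effect gating the group tests, fits the plan's reference to similar effects but remains a reading. The calculation here is also between-group only, without covariates or the test-difficulty factor.

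What none of this answers is that the gate is in the plan and absent from the power statement.

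**Conclusion.** The point holds as a mismatch between the power statement and the planned procedure. The figures .93, .87 and .81 are upper bounds, and power for the gated procedure was not calculated.

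With three outcomes, near-complementary correct and error counts, and the gate read as the group effect, the loss is about 1 point or less at a latency-error correlation of zero or below, and about 5 to 9 points at .7. Latency, with a margin of about 1 point over .80, is marginally under it at a correlation of .2 and about .79 at .3; it keeps falling beyond that. A MANOVA with more outcomes that add little unique information would lose more.

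Every correlation here is an assumption. The sample size is not shown to be wrong; its stated basis is incomplete.

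**What to change.** In Power Considerations, restate each Hypothesis 1 power as the probability that both the MANOVA group effect and the measure's own test are significant. Name the outcomes in the MANOVA, and say in Statistical Plans that the group effect is the gate, if that is intended. Give the powers over a stated range of correlations that includes negative values. Use the archival data for those correlations only where the same participants supplied the measures: the Hypothesis 1 inputs come from two studies, and the plan does not show that latency and error data overlap. The minimum change is to label the three printed figures as upper bounds.

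The cost is a recalculation and somewhat less favourable stated powers. No change to the sample size is needed.

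Removing the gate for the three powered measures is not a free alternative. The gate is the plan's only stated guard against testing many measures, so the sponsor would have to state a replacement multiplicity adjustment and recompute power at that level.

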## Hypothesis

- List the clinical Hypotheses in order of priority:

**Hypothesis 1:** Hyperaroused PI sufferers will show greater performance deficits (slower reaction times; fewer correct responses and more error responses) across repeated daytime testing trials than will age- and gender-matched normal sleepers.

**Hypothesis 2:** Complex reaction time tasks that require executive function, ability to switch attention, and higher order memory function will show greater discrimination of hyperaroused PI sufferers and normal sleepers on measures of mean reaction time, correct response rates and error rates than will simple reaction time tasks.

**Exploratory Aim 3:** To determine the possible sleep deficiencies/mechanisms that contribute to the relative daytime deficits in the hyperaroused PI subgroups we will test measures of sleep continuity (sleep and wake time) and the macro-architecture (sleep stage percentages) and micro-architecture (NREM sleep EEG spectral measures) derived from PSG on nights preceding daytime testing as covariates in study analyses to determine the degree to which they account for observed group differences.

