Hypothesis 2 will be tested via examination of the interaction of the *group factor* (PI vs. NS) and *test difficulty factor* (simple vs. complex) in these analyses. This finding coupled with a posteriori comparisons showing that PI participants have significantly poorer performances than do NS only on the complex tasks will support this hypothesis. Again, elimination of these statistical differences in repeat analyses that use each participant's hyperarousal scale score as a covariate will confirm the role of hyperarousal in explaining the observed group differences on complex tasks.

Our Exploratory Aim will require us to derive a variety of measures from the PSGs conducted on the two nights preceding daytime testing. Following the AASM Scoring Manual guidelines we will score these PSG records and obtain measures of total sleep time, sleep onset latency, wake time after sleep onset, sleep efficiency, and percentages of stages N1, N2, N3, and R for each night. We also will de-artifact each night and then perform a Fast Fourier Transform and subsequent sleep EEG spectral analysis as per our previously published reports to derive NREM absolute and relative spectral power measures in the delta, theta, alpha, sigma, beta and gamma bandwidths. Once these measures are derived for each night, we will compute mean values of these measures for the two PSG nights and then enter those into multivariate regression analyses to determine which measures predict each of the five performance variables used as dependent measures. Those found to be predictive of performance indices will be entered as covariates in the above factorial analyses to determine if any such measures account for the anticipated relative deficits shown by the insomnia group vis a vis the normal group. Since we will anticipate group differences only on the 5 performance measures derived from the set of complex tests, we will plan to test our sleep measures as covariates only in one-way group comparisons using response latency, correct response rate, and error rate data acquired from the complex tests as dependent measures in these analyses. We, thus, will conduct and 5 ANCOVA analyses in which the sleep measures are tested as covariates with each of the 5 performance measures obtained from the complex reaction time tests.

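### Hypothesis 2 is powered on two separate contrasts, not on the interaction that tests it, and its complex-only support rule can succeed at most 46% of the time on latency under the plan's own assumptions

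*Combined protocol and SAP*

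**What the plan says.** In Statistical Plans, "Hypothesis 2 will be tested via examination of the interaction of the" group factor and the test-difficulty factor. That finding is to be combined with a posteriori comparisons: showing that PI participants "have significantly poorer performances than do NS only on the complex tasks will support this hypothesis".

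Power Considerations repeats the point: "Hypothesis 2 entails testing the interaction term showing that difficult reaction time tasks will show significant differences between PI and NS", whereas simple tests are not expected to. It then turns to the contrasts: "Basically this analysis ultimately will entail a posteriori contrasts that show PI vs. NS group differences on complex tasks but not simple tasks". The only power figures for Hypothesis 2 follow, from response latency: "we would have a .80 power to detect the predicted group differences on complex tasks but only .54 power" for the simple tasks, with 82 per group and alpha .05. The section closes by setting enrolment at 82 per group on the strength of these calculations.

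Two other places bear on the rule. The Hypothesis section says that complex tasks "will show greater discrimination of hyperaroused PI sufferers and normal sleepers on measures of mean reaction time, correct response rates and error rates" than simple tasks, which allows a simple-task difference as long as it is smaller. The Exploratory Aim paragraph of Statistical Plans takes the stricter view: "Since we will anticipate group differences only on the 5 performance measures derived from the set of complex tests".

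**The concern.** There are two problems, and solving one does not solve the other.

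**The interaction has no stated power.** The contrast powers answer whether PI and NS differ on each kind of task. The interaction asks whether the difference is larger on complex tasks. It has a smaller effect (a difference of differences) and a different SD. A reader who takes .80 as the power for Hypothesis 2 is relying on a figure for only one part of the rule.

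**The support rule conflicts with the assumptions behind the sample size.** A complex-only pattern requires the simple contrast to be non-significant. The power table, however, assumes a real simple-task difference with about an even chance of detection. If the assumptions are right, the rule fails more often than not, although the claim in the Hypothesis section is true. Enrolling more participants makes this worse, because the simple contrast then reaches significance more often.

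**Working it through.** **Inputs (Power Considerations, Hypothesis 2 table).** Complex latency: PI 496.65, NS 438.14, SD 133.4. Simple latency: PI 247.9, NS 226.4, SD 66.8. There are 82 per group and alpha is .05. Sidedness is not stated; two-sided reproduces the plan's figures, and one-sided does not (.875 and .658). The simple-complex correlation ρ is not given, so it is varied here.

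**Step 1: the plan's own figures.** Two-sample t, 162 df, noncentrality (difference / SD) × √(82/2).
- Complex: 58.51 / 133.4 = .439 SD; power .797 (stated .80).
- Simple: 21.5 / 66.8 = .322 SD; power .535 (stated .54).

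Both are correct as powers of separate two-group contrasts.

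**Step 2: the interaction.** With one simple and one complex composite per person, the test is a two-sample comparison of each participant's complex-minus-simple difference.
- Effect: 58.51 - 21.5 = 37.01 ms.
- SD = √(133.4² + 66.8² - 2ρ × 133.4 × 66.8) = √(22,257.8 - 17,822.24ρ).

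| Assumed ρ | SD of difference (ms) | Power at 82 per group | n per group for 80% |
|---|---|---|---|
| 0 | 149.2 | .35 | 257 |
| .5 | 115.5 | .53 | 154 |
| .7 | 98.9 | .66 | 114 |
| .8 | 89.4 | .75 | 93 |
| .85 | 84.3 | .80 | 83 |
| .9 | 78.9 | .85 | 73 |
| .95 | 73.0 | .90 | 63 |

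Power of 80% at 82 per group needs an SD of about 84 ms or less, that is, ρ of about .85 or more.

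**Step 3: the complex-only rule on latency.** The rule needs the simple contrast to be non-significant. From the plan's own figure, that probability is 1 - .54 = .46. This bounds the rule at any ρ.

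The joint probabilities come from simulation (200,000 studies per ρ, bivariate normal, the plan's means and SDs):

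| Assumed ρ | Interaction and complex significant | Complex significant, simple not | All three conditions |
|---|---|---|---|
| 0 | .35 | .37 | .23 |
| .5 | .53 | .31 | .24 |
| .7 | .65 | .29 | .25 |
| .85 | .75 | .27 | .26 |
| .95 | .80 | .26 | .26 |

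**Step 4: effect of a larger sample.** At ρ = .5 the interaction needs 154 per group. The simple contrast then has noncentrality .322 × √(154/2) = 2.82 and power .80, so the ceiling on the complex-only rule falls from .46 to about .20.

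**The case against.** - **No stated figure is wrong, and the plan is open about powering contrasts on latency.** This is true. The gap is that the test named for Hypothesis 2 has no power figure.
- **The range of .35 to .90 does not show that 82 is too few.** This stands: the interaction is not shown to be underpowered. The range also treats the archival SDs as those of the planned scores. The plan will average three tests of each kind over four trials and "use those composite means in all planned analyses", and it does not say that the archival measures match.
- **Hypothesis 1 supports 82 per group by itself**, with stated powers of .93, .87 and .81. It does, but the same section says that the calculations serve both hypotheses.
- **The support statement could be read as a sufficient condition only.** Taken alone, that sentence could be. It is hard to sustain beside Power Considerations, which builds the absence of a simple-task difference into what Hypothesis 2 entails, and the Exploratory Aim paragraph, which expects the same.
- **The .46 covers latency only.** It does. Hypothesis 2 power for errors, correct responses and the MANOVA cannot be derived from the documents.
- **The sponsor could instead narrow the Hypothesis section to a complex-only claim.** That would make the wording consistent. The rule would still conflict with the assumed 21.5 ms difference, and a non-significant simple contrast at .54 power would be weak evidence of no difference.

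**Conclusion.** Both parts hold.

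- **Interaction power is not established.** On latency, with two-sided alpha .05 and the plan's means and SDs, it lies anywhere from .35 to .90 for assumed correlations of 0 to .95. The calculations therefore do not show whether 82 per group is enough for the test that defines Hypothesis 2.
- **The complex-only rule is at odds with the plan's own data.** On latency it fails at least 54% of the time when the assumed differences are true, whatever the correlation. With all three conditions applied, success is about .23 to .26. Without the simple-task condition it is .35 to .80.

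The first part rests on an unstated correlation and on the archival SDs carrying over to the composites. The ceiling in the second part needs no correlation, only the plan's stated .54. This should be fixed before analysis.

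**What to change.** **Power Considerations**
- Compute the SD of the within-person complex-minus-simple latency difference from the archival data. State the interaction power, or the smallest detectable interaction, at 82 per group. If paired data are not available, show power over a range of correlations.
- Identify .80 and .54 as contrast powers for latency only.
- Say whether the archival tasks match the planned three-test composites. If they do not, note that the SD may not carry over.
- If interaction power is below 80%, say so beside the enrolment statement.

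**Statistical Plans, Hypothesis 2**
- Base support on the interaction estimate with its confidence interval, together with the complex-task group difference.
- Remove non-significance on simple tasks as a condition, in line with the Hypothesis section, and align the matching sentences in Power Considerations.

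**Cost.** One recalculation from data already used, plus wording changes; enrolment and data collection stay the same. The stated power may turn out less favourable, and Hypothesis 2 would no longer claim that simple tasks show no group difference. The change does not itself show that 82 per group is enough for the interaction.
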